9.4.5 Selection and Timing of Dose for Each Subject

E2609 is administered orally, QD, with food. Study treatment will begin on Day 1 following randomization and will continue for approximately 78 weeks.

9.4.6 Blinding

E2609 and placebo will be administered as tablets of identical appearance.

During the Randomization Phase and Follow-Up Phases, subjects, caregivers/informants, and all clinical site personnel involved with the conduct and interpretation of the study, including investigators will be blinded to the treatment codes (double-blind). In order to make decisions about the remainder of the study as well as the full E2609 clinical development program, the sponsor will unblind safety, PK, and PD data on an ongoing basis and perform interim analyses of these data. (revised per Amendment 03)

Every effort should be made to keep the site staff responsible for reviewing laboratory reports and assessing AEs separate from the site staff responsible for the efficacy assessments, particularly for the CDR (ie, those who are trained and certified to perform the various cognitive assessments that are undertaken in this study). Furthermore, at the site, the notes and reports relating to safety assessments must be kept separate from the notes and reports relating to efficacy, particularly for the CDR. (revised per Amendment 01)

Randomization data will be kept strictly confidential, filed securely by an appropriate group with the sponsor or CRO and accessible only to authorized persons (eg, Eisai Global Safety) until the time of unblinding, per the standard operating procedure.

The PK/PD interim analysis to evaluate the E2609 doses to be used for Stage B will be conducted by an independent group (revised per Amendment 02). Any changes to dose will be reflected in an amendment to the protocol and the Statistical Analysis Plan will detail how data will be handled in the primary analysis.

In the event that emergency conditions require knowledge of the study treatment given, the blind may be broken via the code breaker facility within the IxRS. Emergency procedures for revealing drug codes are given in [Section 9.5.4.5](#). If possible, before breaking the blind, the investigator should consult with the sponsor to ascertain the necessity of breaking the code.

At the conclusion of the study, all unused drug supplies are to be returned to the Eisai approved contract packaging vendor.

9.4.7 Prior and Concomitant Therapy

Medication (including over-the-counter medications) or therapy administered to the subject before the study (within 6 months of randomization) and during the study (starting at the date of informed consent) will be recorded on the Prior & Concomitant Medication eCRF or Non-Pharmacological Procedures eCRF. The investigator will record on the Adverse Event eCRF any AE for which the concomitant medication/therapy was administered. If the concomitant medication/therapy is being administered for a medical condition present at the time of entry into the study, the investigator will record the medical condition on the Medical History and Current Medical Condition eCRF.

Listings of prohibited and permitted drugs are provided in [Appendix 2](#). Prohibited medications are presented in [Listing 1](#), [Listing 2](#), [Listing 3](#), [Listing 4](#), [Listing 5](#), and [Listing 6](#). Medications that are permitted with restrictions are listed in [Listing 7](#), [Listing 8](#), and [Listing 9](#).

The following agents are not permitted before randomization (specific timeframes are shown below) and throughout the study until after the last treatment visit:

- Anticoagulants (eg, warfarin, digabatin) are not permitted for a period of 5 half-lives or 7 days (whichever is longer) before randomization
- Drugs which may cause QTc prolongation are not permitted for a period of 5 half-lives or 14 days (whichever is longer) before randomization
- Strong CYP3A4 inhibitors are not permitted for a period of 5 half-lives or 14 days (whichever is longer) before randomization
- Live vaccines are not permitted within 3 months before randomization. This does not apply to non-live/inactivated vaccines
- Ig therapy and biologic drugs are not permitted within 6 months before randomization
- Systemic or ocular immunosuppressive or immunomodulatory drugs are not permitted for a period of 5 half-lives or 60 days (whichever is longer) before randomization

Subjects taking AChEIs or memantine must meet the following criteria in order to be included in the primary analyses:

- On a stable dose for 12 weeks before the Baseline cognitive assessments at Visit 2
- Remain on a stable dose while on study

Subjects who initiate treatment with an AChEI or memantine during the study, or who change their dose of AChEI or memantine while on study, will be allowed to continue in the study, but their clinical efficacy data will be censored from the time of drug initiation for the primary analyses.

Subjects taking all other non-prohibited concomitant medications must meet the following requirements:

- Must be on stable dose for at least 4 weeks before randomization, except for medications that are administered as short courses of treatment or which are to be used intermittently as needed
- Medications that are used as needed, rather than on a stable daily basis, and which are central nervous system (CNS) active and may affect cognitive function, are not permitted during a period of 72 hours before cognitive testing

Subjects who initiate treatment with or have dose adjustment of drugs not intended for treatment of cognitive impairment during the study may continue in the study if in the opinion of the investigator this will not interfere with study procedures or subject safety, and are not prohibited above. If the subject initiates treatment for co-morbidities with a (non-prohibited) drug that may affect cognitive function, the subject should not have cognitive assessments performed until the dose has been stable for at least 4 weeks.

9.4.8 Treatment Compliance

Records of treatment compliance for each subject will be kept during the Treatment Period. CRAs will review treatment compliance during site visits and at the completion of the study.

9.4.9 Drug Supplies and Accountability

In compliance with local regulatory requirements, drug supplies will not be sent to the investigator (or if regionally required, the head of the medical institution or the designated pharmacist) until the following documentation has been received by the sponsor:

- A signed and dated confidentiality agreement
- A copy of the final protocol signature page, signed and dated by both the sponsor and investigator
- Written proof of approval of the protocol, the ICFs, and any other information provided to the subjects by the IRB/IEC for the institution where the study is to be conducted

- A copy of the IRB/IEC-approved ICF and any other documentation provided to the subjects to be used in this study
- The IRB/IEC membership list and statutes or Health and Human Services Assurance number
- A copy of the certification and a table of the normal laboratory ranges for the reference laboratory conducting the clinical laboratory tests required by this protocol
- An investigator-signed and dated FDA Form FDA 1572, where applicable
- Financial Disclosure form(s) for the principal investigator and all subinvestigators listed on Form FDA 1572, where applicable
- A signed and dated curriculum vitae of the principal investigator including a copy of the principal investigator's current medical license (required for United States sites) or medical registration number on the curriculum vitae
- A signed and dated Clinical Trial Agreement (CTA)
- A copy of the regulatory authority approval for the country in which the study is being conducted (if required), and the Import License (if required)

The investigator and the study staff (or if regionally required, the head of the medical institution or the designated pharmacist) will be responsible for the accountability of all study drugs (dispensing, inventory, and record keeping) following the sponsor's instructions and adherence to GCP guidelines as well as local or regional requirements.

Under no circumstances will the investigator allow the study drugs to be used other than as directed by this protocol. Study drugs will not be dispensed to any individual who is not enrolled in the study.

The site must maintain an accurate and timely record of the following: receipt of all study drugs, dispensing of study drugs to the subject, collection and reconciliation of unused study drugs that are either returned by the subjects or shipped to site but not dispensed to subjects, and return of reconciled study drugs to the sponsor or (where applicable) destruction of reconciled study drugs at the site. This includes, but may not be limited to: (a) documentation of receipt of study drugs, (b) study drugs dispensing/return reconciliation log, (c) study drugs accountability log, (d) all shipping service receipts, and (e) documentation of returns to the sponsor. All forms will be provided by the sponsor. Any comparable forms that the site wishes to use must be approved by the sponsor.

The study drugs and inventory records must be made available, upon request, for inspection by a designated representative of the sponsor or a representative of a health authority (eg, FDA, Medicines and Healthcare Regulatory Agency). As applicable, all unused study drugs and empty and partially empty containers from used study drugs are to be returned to the investigator (or if regionally required, the head of the medical institution or the designated pharmacist) by the subject and, together with unused study drugs that were shipped to the site but not dispensed to subjects, are to be returned to the sponsor's designated central or local depot(s) during the study or at the conclusion of the study, unless provision is made by the sponsor for destruction of study drugs and containers at the site. Destruction at the site will only occur under circumstances where regulation or supply type prohibits the return of study

drugs to the central or local depot(s). Approval for destruction to occur at the site must be provided by the sponsor in advance. Upon completion of drug accountability and reconciliation procedures by the site's personnel and documentation procedures by the sponsor's personnel, study drugs that are to be returned to the sponsor's designated central or local depot(s) must be boxed, sealed, and shipped back to the central or local depot(s) following all local regulatory requirements. In some regions, study drugs may be removed from the site and hand delivered to the central or local depot by sponsor representatives. Where study drugs are approved for destruction at the site, destruction will occur following the site's standard procedures and certificates of destruction will be provided to the sponsor.

Drug accountability will be reviewed during site visits and at the completion of the study.

9.5 Study Assessments

9.5.1 Assessments

9.5.1.1 Demography

Subject demography information will be collected at the Screening Visit. Demography information includes date of birth (or age), sex, race/ethnicity, native language, handedness, and highest education level.

9.5.1.2 Baseline Assessments

Assessments to be made at Screening and Baseline and throughout the study are described in [Section 9.5.1.3](#), [Section 9.5.1.4](#), and [Section 9.5.1.5](#).

9.5.1.2.1 MEDICAL HISTORY AND PHYSICAL EXAMINATIONS

Medical and surgical history, current medications including AChEI and memantine use, and current medical conditions will be recorded at the Screening Visit. All medical and surgical history within 10 years must be noted in the Medical History and Current Medical Conditions eCRF. Medical history will include history of cognitive impairment due to AD. Subjects will be asked about history of TB, infections due to varicella zoster virus (chickenpox and herpes zoster/shingles) and HSV Types 1 and 2 (orolabial herpes/cold sores and genital herpes, respectively). The medical history of such infections will include onset, duration, relapse frequency, severity, and treatments. Subjects will also be asked about their vaccination history including vaccinations against varicella zoster virus and TB. The 15-item GDS and modified Hachinski ischemic scale will also be assessed at Screening as part of the exclusion criteria.

Physical examinations (complete or routine) will be performed as designated in [Table 6](#). A complete physical examination will include evaluations of the head, eyes, ears, nose, throat, neck, chest (including heart and lungs), abdomen, limbs, and skin, and a neurological examination. A urogenital examination will only be required in the presence of clinical symptoms related to this region. Documentation of the physical examination will be included in the source documentation at the site. Significant findings at the Screening Visit

will be recorded on the Medical History and Current Medical Conditions eCRF. Changes from screening physical examination findings that meet the definition of an AE will be recorded on the Adverse Events eCRF.

9.5.1.2.2 VIRAL TESTING

As specified in [Table 6](#), blood will be collected for screening for Hepatitis B and Hepatitis C for determining eligibility, and at Baseline for viral characterization.

9.5.1.2.3 B12 TESTING

Blood will also be collected for vitamin B12 levels as specified in [Table 6](#).

9.5.1.2.4 TB EXPOSURE TESTING

Blood will also be collected for testing for previous TB exposure, as specified in [Table 6](#).

9.5.1.2.5 URINE DRUG TESTING

Urine will be collected for drug screening as specified in [Table 6](#).

9.5.1.3 Efficacy Assessments

9.5.1.3.1 PSYCHOMETRIC ASSESSMENTS

The timing of psychometric assessments is shown in [Table 6](#) and [Table 7](#). These assessments should be administered in the morning (or, if not possible, consistently at the same time of day) and should be completed before more invasive assessments or procedures (eg, physical examination, ECG, blood draws). At the Screening Visit, the recommended order of assessments is: MMSE, ISLT (immediate recall), CBB, ISLT (delayed recall), CBB (repeat CBB for additional practice), CDR, and FAQ. The CBB may be repeated multiple times if required for the subject to pass completion and integrity criteria. At the Baseline Visit, the assessments are to be conducted in the following order: MMSE, CDR, ADAS-cog₁₄, FAQ, ISLT (immediate recall), CBB, and ISLT (delayed recall). (revised per Amendment 02)

At visits where the CDR or FAQ are conducted, the investigator will determine whether the caregiver or informant must attend in person or whether telephone contact will be suitable, and will base this determination upon the functional ability of the subject among other factors.

The Derived Alzheimer's Disease Composite Score: The primary efficacy endpoint is the change from baseline in the derived ADCOMS at 18 months of treatment in MCI/Prodromal subjects.

The ADCOMS is derived from the ADAS-cog (4 items), the MMSE (2 items), and the CDR (all 6 items), described below. The ADCOMS is more sensitive to clinical progression compared with currently existing clinical batteries and requires smaller sample sizes for clinical studies in MCI/Prodromal AD or mild to moderate AD. (revised per Amendment 01)

It also shows sensitivity to treatment effects with AChEIs. The ADCOMS assesses both cognitive and functional domains and can be offered as a single primary clinical endpoint. The ADCOMS has a range from 0 to 1.97.

CogState Brief Battery: The CBB is a computer-based battery comprising 4 cognitive tests:

1. Detection – a simple reaction time test where the subject presses a key when the card is turned face up from a pack of cards (“Has the card turned over”). Speed of response is the measure.
2. Identification – a simple choice reaction time test where the subject presses 1 of 2 keys when the card just turned face up is either a red card or a black card (“Is the card red”). Speed of response is the measure.
3. One Card Back – a simple working memory test where the subject presses 1 of 2 keys when the card turned face up is either the card seen in the immediately previous trial or not (“Is the previous card the same”). Accuracy of response is the measure.
4. One Card Learning – a visual learning and memory test where the subject presses 1 of 2 keys depending on whether the card just turned face up has been seen before or not in the task (“Have you seen this card before in this task”). Accuracy of response is the measure.

ISLT: The ISLT is a verbal learning and episodic memory test assessing both immediate and delayed recall. Subjects are read a list of 12 items that can be obtained at the local shopping center. Subjects are asked to recall as many of the items as possible and this immediate recall trial is repeated 3 times. After a delay of approximately 15 minutes, in which time the CBB is performed, subjects are again asked to recall as many of the words on the shopping list as they can (ie, a delayed recall trial).

Mini Mental State Examination: A 30-point scale that measures orientation to time and place, registration, immediate and delayed recall, attention, language, and drawing. Scores range from 0 (most impaired) to 30 (no impairment).

Clinical Dementia Rating: The CDR assesses 6 domains of subject function; memory, orientation, judgment and problem solving, community affairs, home and hobbies and personal care. Each of these items has a maximum possible score of 3 points and the total score is a sum of the item scores (sum of boxes) giving a total possible score of 0 to 18 with higher scores indicating more impairment.

Alzheimer's Disease Assessment Scale - cognitive subscale: Discussed in [Section 9.2.4](#).

Functional Assessment Questionnaire: Either a caregiver or informant or the subject provides performance ratings (from 0 to 3) on 10 complex activities of daily living performed within the preceding 4 weeks. Scores range from 0 (independent) to 30 (dependent).

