9.7.1.6.3 EXPLORATORY EFFICACY ANALYSES

(revised per Amendments 01 and 02)

An MMRM will be used to analyze the following exploratory endpoints:

- Change from baseline in the derived ADCOMS at 12 months in MCI/Prodromal and mild to moderate AD subjects
- Change from baseline in total hippocampal atrophy at 12 and 18 months in mild to moderate AD subjects as measured by vMRI
- Change from baseline in CSF A β (1-x) and CSF A β (1-42) after 4 weeks and 18 months in MCI/Prodromal and mild to moderate AD subjects. Data from early discontinuations will also be included.
- Change from baseline in the clinical assessments: ADAS-cog, CDR, MMSE, ISLT, CBB, and FAQ at 12 weeks and at 6, 9, 12, 15, 18, 19, and 21 months in MCI/Prodromal and mild to moderate AD subjects
- Change from baseline in plasma and CSF amyloid and CSF BACE1 measurements after 4 weeks and 18 months of treatment, and during posttreatment follow-up in MCI/Prodromal and mild to moderate AD subjects
- Change from baseline in left and right hippocampal, whole brain, and total ventricular volume at 6, 12 and 18 months as measured by vMRI in MCI/Prodromal and mild to moderate AD subjects

A linear mixed-model will be used to analyze the following exploratory endpoints:

- Change from baseline in brain amyloid levels as measured by amyloid PET at 18 months in MCI/Prodromal and mild to moderate AD subjects
- Change from baseline in CSF biomarkers of neurodegeneration (eg, tau, p-tau) at 18 months of treatment in MCI/Prodromal and mild to moderate AD subjects

Data from early discontinuations will also be used as appropriate. Comparisons between each treatment group and placebo will be performed.

A linear mixed-model with repeated measures will be used to determine the relationship between the following endpoints:

- Change from baseline in the derived ADCOMS score and the change from baseline in biomarkers in CSF at 18 months in MCI/Prodromal and mild to moderate AD subjects
- Change from baseline in the derived ADCOMS score and change from baseline in imaging biomarkers (hippocampal, whole brain, and total ventricular volumes) at 12 and 18 months in MCI/Prodromal and mild to moderate AD subjects

ApoE status for heterozygous and homozygous E4 carriers will be included in the model to assess the effect of *ApoE* status in this relationship.

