Derived ADCOMS: The derived ADCOMS represents a new approach to the analysis of selected items (12 total) from 3 fully validated and well established clinical tools, the ADAS-cog (4 items), the MMSE (2 items), and the CDR (all 6 items). The 3 scales should be administered in full in the

morning, or, if not possible, consistently at the same time of day.

Alzheimer's Disease Assessment Scale - cognitive subscale: The 14-item version will be used since it is considered more relevant for subjects with MCI/Prodromal AD or mild AD.

Mini Mental State Examination: A 30-point scale that measures orientation to time and place, registration, immediate and delayed recall, attention, language, and drawing.

Clinical Dementia Rating: Assesses 6 domains of subject function; memory, orientation, judgment and problem solving, community affairs, home and hobbies, and personal care.

CogState Brief Battery: A computer-based battery comprising 4 cognitive tests:

1. Detection – a simple reaction time test. Speed of response is the measure.
2. Identification – a simple choice reaction time test. Speed of response is the measure.
3. One Card Back – a simple working memory test. Accuracy of response is the measure.
4. One Card Learning – a visual learning and memory test. Accuracy of response is the measure.

International Shopping List Task: The ISLT is a verbal learning and episodic memory test assessing both immediate and delayed recall.

Functional Assessment Questionnaire: The FAQ has 10 items concerned with performing daily tasks necessary for independent living. Either a caregiver or informant or the subject provides performance ratings on 10 complex activities of daily living performed within the preceding 4 weeks.

Volumetric Magnetic Resonance Imaging: vMRI will be used to evaluate disease modification, including the change from Baseline in terms of the measured hippocampal volume based upon the centralized measurement of the structure on repeated MRIs.

Pharmacokinetic Assessments

Blood samples will be collected for the determination of the concentrations of E2609. For subjects who consent to CSF sample collection, CSF samples will be collected for the determination of E2609 concentrations. (revised per Amendment 02) Analyses of metabolite concentrations may be performed depending on emerging data from other studies with E2609.

Pharmacodynamic, Pharmacogenomic, and Other Biomarker Assessments

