9.3.1 Inclusion Criteria

Subjects must meet all of the following criteria to be included in this study:

1. Meets the core clinical research criteria of the NIA-AA for MCI due to AD ([Albert, et al., 2011](#)) or AD dementia ([McKhann, et al., 2011](#)) and is "staged" or classified as either MCI or mild to moderate dementia and also complies with the following: (revised per Amendment 01)

Required at Screening Visit 1:

(revised per Amendment 02)

- a. Subjective Memory Complaint with evidence of concern about a decline in cognition from the subject, informant, or clinician's observation
- b. Cognitive impairment of at least 1 SD from age adjusted norms in delayed recall on the ISLT. Alternatively, cognitive impairment of at least 0.5 SD from age-adjusted

- norms in delayed recall on the ISLT plus impairment of at least 1 SD from age-adjusted norms in at least 1 other computerized learning and memory test (ISLT immediate recall, or 1 of the learning and memory components of the CBB). (revised per Amendment 02)
- c. FAQ ≤ 24 (revised per Amendment 01)
 - d. MMSE ≥ 16 (revised per Amendment 01)
2. Amyloid positive PET image based on centralized PET scan reading; an historical amyloid positive PET scan may be used if conducted within the previous 12 months and provided that the scan and result are considered acceptable by the central PET reading group (revised per Amendment 02)
 3. Male or female, age 50 to 85 years, inclusive at time of consent

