 4. Must have an identified caregiver or informant who is willing and able to provide follow-up information on the subject throughout the course of the study. This person must, in the opinion of the investigator, spend sufficient time with the subject on a regular basis such that the caregiver or informant can reliably fulfill the study requirements and must provide separate written consent. The caregiver or informant need not be living in the same residence as the subject. If the caregiver or informant is not residing with the subject, the investigator has to be satisfied that the subject can contact the caregiver or informant readily during the times when the caregiver or informant is not with the subject. If in doubt about whether a subject's care arrangements are suitable for inclusion, the investigator should discuss this with the medical monitor. At visits where the CDR or FAQ are conducted, caregivers or informants need to either attend the visit in person along with the subject or be able to be contacted by telephone at the time of the visit. The investigator will determine whether attendance in person is required or whether telephone contact will be suitable and will base this determination upon the functional ability of the subject among other factors.
 5. If receiving acetylcholinesterase inhibitor (AChEIs) or memantine, must have been on a stable dose for at least 12 weeks before the Baseline cognitive assessments at Visit 2, with no plans for dose adjustment in the foreseeable future. Treatment-naïve subjects can be entered into the study but there should be no plans to initiate treatment with AChEIs or memantine at the time of entry into the study.
 6. Must have been on stable doses of all other permitted chronically used concomitant medications (ie, not related to their cognitive decline) for at least 4 weeks before randomization

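### The FAQ may be rated by the subject instead of the informant, with no rule on keeping the respondent the same, so the FAQ entry limit and the exploratory FAQ change scores can depend on who answered

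*Protocol*

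**What the plan says.** Section 9.5.1.3.1 describes the FAQ in these terms: "Either a caregiver or informant or the subject provides performance ratings (from 0 to 3) on 10 complex activities". The score is bounded: "Scores range from 0 (independent) to 30 (dependent". The synopsis, under Efficacy Assessments, repeats the respondent rule: "Either a caregiver or informant or the subject provides performance ratings on 10 complex activities of daily living performed within the preceding 4 weeks".

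The FAQ has two main uses:

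- **Entry.** Inclusion criterion 1 in Section 9.3.1 sets "FAQ ≤ 24 (revised per Amendment 01") as a Screening requirement, beside "MMSE ≥ 16 (revised per Amendment 01").
- **Analysis.** Section 9.7.1.6.3 lists, for an MMRM, "Change from baseline in the clinical assessments: ADAS-cog, CDR, MMSE, ISLT, CBB, and FAQ at 12 weeks" and at seven later time points (6, 9, 12, 15, 18, 19 and 21 months). This is an exploratory endpoint in Section 9.7.1.1.3.

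The FAQ is also summarised as a baseline variable (Section 9.7.1.4).

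On informant availability, inclusion criterion 4 states that, at visits with the CDR or FAQ, "caregivers or informants need to either attend the visit in person along with the subject or be able to be contacted by telephone". Sections 9.1.1.1 and 9.1.1.2 require the informant to be present at Screening and at Baseline.

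**The concern.** The FAQ asks how the subject managed complex daily activities over the previous four weeks. Entry reaches into moderate dementia, and Section 5.3 provides for subjects who lack capacity to consent. As written, such a subject may be the only source of the rating.

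Two things are at stake. First, a change from baseline is interpretable only if both ends are measured in the same way. If a subject self-rates at one visit and an informant rates at another, the change score contains any difference between the two raters as well as any change in function. Second, the FAQ limit is meant to cap severity at entry. A subject who reports less difficulty than the informant would report can pass a limit that the informant's rating would not.

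The protocol gives the FAQ some interpretive weight: Section 9.2.4 ranks it above cognitive change as a sign of clinical meaning. It also makes an informant available at every FAQ visit, so nothing is gained by allowing self-rating.

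**Working it through.** The protocol states no figure that can be reproduced here. It gives no FAQ standard deviation, no expected FAQ effect and no agreement between respondents. The check is a reading of the passages side by side, followed by an illustration on stated assumptions.

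**1. Is the respondent fixed anywhere?** Section 9.5.1.3.1 and the synopsis give the same open choice. The footnotes to Tables 6 and 7 fix the time of day and the order of tests, and leave to the investigator whether the informant attends or is telephoned. They do not say who answers the FAQ. Criterion 4 makes the informant available without making that person the respondent. For the CDR, by contrast, Section 9.2.4 names both subject and informant as interviewees. No text restricts self-rating, asks for the same respondent across visits, or asks for the respondent to be recorded.

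**2. Are comparable sources of variation fixed elsewhere?** Yes. Cognitive tests are held to a consistent time of day, blood pressure to the same arm and preferably the same measurer (Section 9.5.1.5.4), and the PET agent is unchanged within a subject (Table 6, footnote l). The FAQ respondent has no such rule.

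**3. Where does the FAQ enter?**

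| Use | FAQ involved? | Place |
|---|---|---|
| ADCOMS (primary endpoint) | No: ADAS-cog, MMSE and CDR items only | 9.5.1.3.1 |
| Secondary endpoints | No | 9.7.1.1.2 |
| Success, futility, adaptive allocation | No: ADCOMS only | 9.7.1.6, 9.7.3 |
| Sample size | No | 9.7.2 |
| Entry limit at Screening | Yes | 9.3.1 |
| Exploratory change from baseline, 8 time points | Yes | 9.7.1.1.3, 9.7.1.6.3 |

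Scale check: 10 items × 3 = 30, which agrees with the stated range. The entry limit is 24/30 = 80% of the maximum.

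**4. What could a switch do? (Illustration only.)** Assume a gap g of 2 to 5 points between self-rating and informant rating, and a share p of 10% to 20% of subjects who switch respondent between Baseline and Month 18. Neither figure comes from the protocol, and nor does the direction of the gap.

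- Shift in one arm's mean change = p × g: from 0.10 × 2 = 0.2 to 0.20 × 5 = 1.0 points.
- Added variance, if switching is unrelated to true change, = p(1 − p)g²: from 0.10 × 0.90 × 4 = 0.36 to 0.20 × 0.80 × 25 = 4.0.
- Shift in the difference from placebo = g × (p in the active arm − p in the placebo arm). With equal switching this is zero.

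**5. What could self-rating do at entry? (Same assumed gap.)** A subject whom the informant would score 27, and who under-reports by 2 to 5 points, would self-rate 22 to 25. That meets the limit of 24 when the gap is 3 points or more.

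**The case against.** The strongest reply is that the wording permits self-rating without expecting it. The surrounding text is built around the informant: one is identified for the whole study, must be present at Screening and Baseline, and must attend or be reachable at every later FAQ visit. A switch from self-rating at Baseline to informant rating at Month 18 would mean passing over an informant who is in the building. This stands as a point about likelihood. It does not close the gap in the rule, because presence does not settle who answers.

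The second reply is that little rests on the FAQ. This also stands. The endpoint is exploratory, and the entry limit works alongside MMSE, NIA-AA clinical criteria and staging, and ISLT impairment.

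A reader might infer that respondent switching biases the treatment comparison, for example because subjects who decline faster move to informant rating sooner. The protocol does not support that step. Allocation is randomised, and subjects and site staff are blinded (Section 9.4.6). With no drug effect, switching should be similar across arms and largely cancel. If switching did follow decline, it could change the size of a difference that already exists, but no route to a spurious one is apparent. A reader might also take 0.2 to 1.0 points as an estimate. It is the product of assumed inputs and applies to a single arm's mean.

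**Conclusion.** The point holds as a weakness in a measurement rule. The FAQ entry limit and the exploratory FAQ change scores can depend on self-rating by cognitively impaired subjects and on which person answered at each visit. The probable consequence is added noise in FAQ change and a softer severity cap.

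The size is unknown. It depends on how often self-rating is used and on the gap between raters, and the protocol gives neither. Bias between arms has not been shown. The primary endpoint, the Bayesian decision rules and the sample-size rationale are unaffected. Calling the FAQ results dependent on self-rating, without the qualifier that they can be, would go beyond the text.

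This is a cheap improvement. It belongs in the protocol because it is an instruction to sites: a later analysis plan cannot recover a respondent who was neither fixed nor recorded.

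**What to change.** In Section 9.5.1.3.1 and the synopsis, remove the subject as a permitted FAQ respondent and add text such as: *The FAQ, including the Screening FAQ used for eligibility, is completed by the caregiver or informant identified under inclusion criterion 4, by the same person at all visits where possible. The respondent is recorded at each visit.*

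Some subjects may already have rated themselves at Baseline; Appendix 5 shows that screening had begun. For them, flag the respondent at each visit so that the corrected rule does not itself create an unnoticed switch in the change score.

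The cost is a small change of wording in two places, a short instruction to sites and one recorded field. No visits or staff are added, because criterion 4 already requires the informant to attend or be reachable whenever the FAQ is done.
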